### 19.4. ECG Evaluations

The following summaries will be provided for ECG data:

A by-patient listing of all ECG data collected in the 'ECG' form of the eCRF.

## 19.5. Immunogenicity Analysis

The assay includes three tiers of analysis designated as screening, confirmation, and titration, respectively. Samples identified as positive in the screening assay will be tested in a confirmatory assay that employs a 0.1% false positive rate. Confirmed positive samples will be further evaluated for ADA titer. Neutralizing capacity (Nab) of the antibodies will be evaluated for samples in which anti-drug antibodies have been confirmed to be present.

Immunogenicity data, including subject ID, visit, anti-drug antibody (ADA) results, ADA titers, and neutralizing antibody results (Nab) will be presented.

Immunogenicity to adalimumab will be descriptively summarized by treatment group at Week 28 time point and include:

- Incidence of positive ADA and NAb response
- Titer of subjects with positive ADA response
- Change from Week 12 in ADA and NAb incidence, and ADA titer

Document: \\ieedc-vnasc01\Biosdata\Viatris\HULIO\HAB34991\Biostatistics\Documentation\SAP

Author: Version Number: 2.0

Version Date: 29Nov2023

Template No.: CS\_TP\_BS016 Revision 7 Reference: CS\_WI\_BS005

Page 37 of 48

# 19.6. Vital Signs

The following Vital Signs measurements will be reported for this study:

- Systolic Blood Pressure (mmHg)
- Diastolic Blood Pressure (mmHg)
- Heart Rate (bpm)
- Respiratory Rate (breaths/min)
- Body Temperature ( C)

The summary of actual and change from baseline by visit will be provided for vital sign data. In case of multiple measurement timepoints at one visit, the pre-injection data will be used for summary tables.

Vital signs data will be listed.

# 19.7. Physical Examination

The following summaries will be provided for physical examination data:

A by-patient listing of physical examination data as recorded in the 'Physical Examination' form of the eCRF.

# 19.8. Other Safety Assessments

The following summaries will be provided:

- A by-patient listing of Chest X-Ray data as recorded in the 'Chest X-Ray' form of the eCRF.
- A by-patient listing of pregnancy test data at screening visit as collected in the 'Pregnancy' form of the eCRF.
- A by-patient listing of serology test data at screening visit as collected in the 'Laboratory Assessment: Serology (HBsAg, HBcAb, HCVAb, HIV)' form of the eCRF.
- A by-patient listing of IGRA or Purified Protein Derivative Test data at screening visit as collected in the 'Laboratory Assessment: IGRA or Purified Protein Derivative Test' form of the eCRF.
- A by-patient listing of Urine Drug Screen data at screening visit as collected in the 'Laboratory Assessment: Urine Drug Screen' form of the eCRF.
- A frequency table for the injection site reactions: pain, tenderness, erythema/redness, induration/swelling, and pruritus (itching) will be presented along with a by-patient listing as collected in the 'Injection Site Reaction -Investigator Assessment' form of the eCRF.
- A by-patient listing of the monitor for signs and symptoms of TB and other serious infections, for progression to

Document: \\ieedc-vnasc01\Biosdata\\Viatris\HULIO\HAB34991\Biostatistics\Documentation\SAP

Author: Version Number: 2.0

Version Date: 29Nov2023

Template No.: CS\_TP\_BS016 Revision 7 Reference: CS\_WI\_BS005

Page 38 of 48

NYHA Class III/IV Heart failure2, and examination for non-melanoma skin cancer will be presented as recorded in the 'Signs and Symptoms' form of the eCRF.

# 20. PHARMACOKINETIC ANALYSIS

All PK analyses will be performed on the Pharmacokinetic Population (PKP).

Descriptive statistics of plasma concentrations and PK parameters will be also done on PKP. For PK parameter analysis on Run-in Period Population (RPP) the same rules regarding exclusion as for PKP will be applied.

#### 20.1. General Pharmacokinetic considerations

The PK parameters will be calculated according to the Viatris SOP GCRD-GPK-0030 'Standard Pharmacokinetic Parameter Definitions and Calculations'.

The actual sampling times will be used for the calculation of PK parameters, except the first (Predose) and the last time point (Predose before next dose) for each intensive PK intervals (Week 10-12 and Week 26-28). If the first time point is within 12 hours before dosing of Week 10 or Week 26 then the time will be set to 0 for PK parameter calculation purpose. Should the PK blood sample collected during the final timepoints, either Week 12 or Week 28, after 506 hours following the preceding dose, the PK concentration values for that sample at Week 12 or 28 will be marked as missing. Consequently, such samples will be excluded from the calculation of PK parameters. When the Week 12 or 28 PK blood sample is missing (including those treated as missing due to large time deviations as define above), the PK concentration will be extrapolated using two previous PK concentration values using log linear method. When the Week 12 or 28 PK blood sample is not missing but the time deviations is more than 12 hours, the PK concentration at 336 hours will be determined for AUC calculation purpose. This will be achieved through interpolation or extrapolation using the log-linear method, with interpolation being the preferred method if feasible. If the PK blood sample at Week 12 or 28 is not missing and the time deviation is within 12 hours, the time will be standardized to 336 hours for the purpose of AUC calculation.

Concentrations used in the PK analysis will be in mcg/mL, instead of ng/mL as reported in bioanalytical report.

If a measured level for a given PK sample is BLQ then 1/2 LLOQ of the assay will be used for the PK parameter calculation purpose. For samples taken at baseline (visit 1) BLQ values will not be replaced by 1/2 LLOQ but reported as 0 instead.

Document: \\ieedc-vnasc01\Biosdata\Viatris\HULIO\HAB34991\Biostatistics\Documentation\SAP

Author: Version Number: 2.0

Version Date: 29Nov2023

Template No.: CS\_TP\_BS016 Revision 7 Reference: CS\_WI\_BS005

Effective Date: 01Nov2021

Page 39 of 48

# 20.2. Pharmacokinetic Endpoints

#### 20.2.1. Primary Pharmacokinetic Variables

Pharmacokinetics will be assessed as the primary objective in this trial.

The primary pharmacokinetic endpoints are:

- AUCτ, 26-28 (Area under the adalimumab plasma concentration-time curve over the dosing interval of Week 26-28)
- Cmax, 26-28 (Maximum observed adalimumab plasma concentration during the dosing interval of Week 26-28)

#### 20.2.2. Secondary Pharmacokinetic Variables

The secondary pharmacokinetic endpoints are:

- Cmin, 26-28 (Minimum observed adalimumab plasma concentration during the dosing interval of Week 26-28)
- Tmax, 26-28 (Time to maximum observed adalimumab plasma concentration during the dosing interval of Week 26-28)

### 20.2.3. Handling of Missing Data

If actual PK sampling date is missing, the dosing date of the same visit will be used instead.

If actual dosing date is missing, the PK sampling date of the same visit will be used instead.

If actual dosing time is missing and the dosing and PK sampling dates are identical then the PK sampling time of the same visit will be used instead.

If actual PK sampling time for pre-dose PK samples is missing and the dosing and PK sampling dates are identical then the dosing time of the same visit will be used instead.

If actual PK sampling time for sub-visits 6a-c or 14a-f is missing, the clock-time of preceding dosing will be used instead.

If it is not possible to impute missing date or times, the respective date or time will stay missing.

#### 20.2.4. Duplicated PK samples

There are duplicated PK sample collected by clinic and analyzed by bioanalytical lab, the PK concentration values from the same samples will be averaged as the single PK sample collection and the correct time will be used.

Document: \\ieedc-vnasc01\Biosdata\Viatris\HULIO\HAB34991\Biostatistics\Documentation\SAP

Author: Version Number: 2.0

Version Date: 29Nov2023

Template No.: CS\_TP\_BS016 Revision 7 Reference: CS\_WI\_BS005

Effective Date: 01Nov2021

Page 40 of 48

#### 20.2.5. Unscheduled PK samples

There are unscheduled PK sample collected by clinic and analysed by bioanalytical lab, those sample will be used by the actual time sample was collected for PK parameter calculation purpose.

#### 20.2.6. Analysis of Pharmacokinetic Endpoints

Descriptive statistics of plasma concentrations and PK endpoints, as well as the tables and graphs for the pharmacokinetic noncompartmental analyses, will follow specific definitions in this SAP.

#### 20.2.7. Analysis of Primary Pharmacokinetic Endpoints

Pharmacokinetic parameters of a patient will be included in the statistical analyses of PK endpoints (ANCOVA) if they are not flagged for exclusion due to a major protocol violation relevant to the evaluation of PK.

The primary objective of this trial is to test the hypothesis of PK similarity between the switching arm and continuous Humira® arm on the two PK parameters: AUC $\tau$ , 26-28 and Cmax, 26-28.

The test for PK similarity will be performed with respect to the switching vs. continuous Humira® arm. For the primary endpoint analysis, the BE margins 80% - 125% on the ratio will be applied.

The hypotheses for the primary endpoint analysis can be written as follows:

- H0: Ratio of the means of AUCτ, 26-28 (switching arm versus continuous Humira® arm) is less than 80% or more than 125%
- H1: Ratio of the means of AUCτ, 26-28 (switching arm versus continuous Humira® arm) is within [80%, 125%]
- and
- H0: Ratio of the means of Cmax, 26-28 (switching arm versus continuous Humira® arm) is less than 80% or more than 125%
- H1: Ratio of the means of Cmax, 26-28 (switching arm versus continuous Humira® arm) is within [80%, 125%]

•

Two one-sided tests of significance level of 5% was chosen to ensure overall type I error control at 5% per the current regulation standard.

The two endpoints are considered coprimary (i.e., the trial is considered positive if the results for both endpoints are simultaneously positive), therefore no multiplicity-adjustment with respect to the alpha level will be performed.

Document: \ivedc-vnasc01\Biosdata\Viatris\HULIO\HAB34991\Biostatistics\Documentation\SAP

Author: Version Number: 2.0

Version Date: 29Nov2023

Template No.: CS\_TP\_BS016 Revision 7 Reference: CS\_WI\_BS005

Page 41 of 48

It is well known that adalimumab can trigger ADA response which in turn leads to reduced exposure and extreme low Pk parameter values. Log-transforming the PK parameter values with extreme low values will skew the normal distribution. Similarly, Voltarire-X trial has used the same approach of non-log-transformed PK for primary analysis due to the same reason stated above. Hence the use of the original scale is considered reasonable and proposed in this study. Fieller's theorem will be used to calculate CIs of the ratio without log-transforming of PK parameter values.

The statistical model used for the analysis of AUCτ, 26-28 and Cmax, 26-28 will be an analysis of covariance (ANCOVA) model. This model will include effects accounting for:

- Treatment (switching arm versus continuously Humira® arm)
- Natural Logarithm of rPASI, where rPASI is the ratio of PASI at Week 12 and PASI at Week 1 (continuous
- value as covariate variable). If PASI at Week 12 is zero, then the score for Week 12 will be set to 0.05 (otherwise
  the logarithm is not defined). Note that this imputation is only done for the purpose of creating the covariate used
  in this PK analysis
- Weight at screening period (continuous value as covariate variable)
- AUCτ, 10-12 or Cmax, 10-12 (continuous value as covariate variable)

as a source of variation. As the measurements at Week 12 will be prior to randomization and all subjects will have received the same treatment with the reference treatment only, the covariates listed above are all considered adequate baseline values.

All effects will be considered as fixed. The model is described by the following equation:

response (AUC $\tau$ , 26-28 or Cmax, 26-28) = overall mean + Ln(rPASI) + weight at screening period + (AUC $\tau$ , 10-12 or Cmax, 10-12) + treatment effect + random error

where the random errors are assumed to be independent and normally distributed with zero mean and variance  $\sigma^2$ . The analysis will be adjusted for the covariates as stated in above model which will be implemented with the SAS® procedure PROC MIXED in conjunction with the LSMEANS statement. The LSMEANS statement is used to estimate the treatment LSMeans of the switching and non-switching arms which will be used to construct the point estimate for the ratio of means. The CI will be derived based on Fieller's theorem.

Equivalently to rejecting both null hypotheses for the primary endpoints, PK similarity between Switching arm and Continuous Humira® arm will be concluded if the two-sided 90% Fieller CI for the ratio of the means is fully contained within the standard equivalence limits of 80.00% to 125.00%.

Document: \\ieedc-vnasc01\Biosdata\\Viatris\HULIO\HAB34991\Biostatistics\Documentation\SAP

Author: Version Number: 2.0

Version Date: 29Nov2023

Template No.: CS\_TP\_BS016 Revision 7 Reference: CS\_WI\_BS005

Page 42 of 48

### 20.2.8. Analysis of Secondary PK endpoint

The secondary PK endpoint Cmin, 26-28 will be analysed in the same way as the primary endpoints. However, only the mean ratio and CIs will be calculated and presented. The 90% Fieller CI will not be required to be within the 80.00% to 125.00% limits.

The secondary PK endpoint tmax, 26-28 will be analyzed in a descriptive manner only.

### 20.2.9. Sensitivity Analysis of PK endpoints

A similar model as the primary PK endpoint analysis will be performed on the natural log-transformed (Ln) PK endpoints as sensitivity analysis.

The model is described by the following equation:

Ln (AUCτ, 26-28, Cmax, 26-28 or Cmin, 26-28) = overall mean + Ln(rPASI) + weight at screening period + Ln (AUCτ, 10-12, Cmax, 10-12 or Cmin, 26-28) + treatment effect + random error.

The 90% CIs will be generated from the above model to further support BE equivalency.

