Sensitivity Analyses: The AUC τ , $_{26\text{-}28}$ and C_{max} , $_{26\text{-}28}$ will be analysed using analysis of covariance (ANCOVA) model on the log transformed scale. This model will include treatment and covariates. Log transformed AUC $_{\tau,\ 10\text{-}12}$ or $C_{max,\ 10\text{-}12}$ will be used as covariates.

The secondary PK endpoint $C_{min\ 26-28}$ will be analyzed in the same way as the primary endpoints. However, even the mean ratio and CIs will be calculated and presented. No formal conclusion is required to be within BE limits.

The secondary PK endpoint $T_{max\ 26-28}$ will be analyzed in a descriptive manner only.

All PK analysis will be performed on the PK population.

Efficacy Analysis:

All secondary efficacy endpoint analyses will be based on the PP population.

The difference in proportions will be calculated as the difference between the observed proportions in each treatment group. An asymptotic 2-sided 90% confidence interval for the difference of proportions will be obtained using the Wald method.

Safety Analyses:

Treatment-emergent AEs, serious AEs and Adverse event of special interest (AESI) will be descriptively summarized by system organ class, preferred term, and treatment group.

Overall, descriptive summaries will be produced as well as according to severity and relationship to the study treatment.

Local tolerance and antibodies to adalimumab will be descriptively summarized by treatment group.

The safety analyses will be performed on the Safety and Run-in Period populations.

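### The log-scale sensitivity model for Cmin uses Cmin at Weeks 26-28 as its own covariate, so as written it cannot estimate a treatment effect

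*SAP*

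**What the plan says.** SAP section 20.2.9 plans a log-scale counterpart of the primary ANCOVA and writes one equation for all three endpoints. The responses are the logs of AUCτ, Cmax and Cmin at Weeks 26-28. The PK covariates, in the same order, are the logs of AUCτ at Weeks 10-12, Cmax at Weeks 10-12 and Cmin at Weeks 26-28; the equation ends "10-12, Cmax, 10-12 or Cmin, 26-28) + treatment effect + random error".

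The related passages are these:

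- **SAP 20.2.7** (primary model) lists the PK covariate as "AUCτ, 10-12 or Cmax, 10-12 (continuous value as covariate variable". It accepts its covariates as baselines because they precede randomization. The Pharmacokinetic Analysis part of the protocol synopsis likewise says that every covariate is measured before randomization.
- **SAP 20.2.8** says of the untransformed scale: "The secondary PK endpoint Cmin, 26-28 will be analysed in the same way as the primary endpoints". It names no covariate. It adds that "The 90% Fieller CI will not be required to be within the 80.00% to 125.00% limits", and the protocol synopsis agrees: "No formal conclusion is required to be within BE limits".
- **SAP 20.2.2** defines Cmin only as "Minimum observed adalimumab plasma concentration during the dosing interval of Week 26-28".
- **Protocol synopsis, Sensitivity Analyses**, covers only AUC and Cmax, each with its log-transformed Week 10-12 covariate.

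**The concern.** The third covariate in the 20.2.9 equation is the response itself. It is measured after randomization, which conflicts with the rule on covariates in both documents. It also leaves the model nothing to estimate.

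Section 20.2.9 says its intervals are meant to give further support to equivalence. For Cmin, a program that followed the equation would print perfect agreement or an error, and neither is evidence. Section 20.2.7 explains why scale matters here: anti-drug antibodies can produce extremely low PK values, which behave differently on the log and untransformed scales. A log-scale check of Cmin is therefore worth having, and this is the only sensitivity analysis planned for Cmin. If the fault comes to light only in the output, the replacement covariate would be chosen after unblinding.

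**Working it through.** **Result of the equation as printed.** The plan states no figure for Cmin to reproduce; the result follows from the equation alone. Write y = Ln(Cmin,26-28). The printed model is

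y = b0 + b1·Ln(rPASI) + b2·weight + b3·y + τ·treatment + error.

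1. Set b3 = 1 and all other coefficients to 0. Every residual is then y − y = 0.
2. The residual sum of squares is 0, which no other fit can improve on. The solution is unique unless y happens to be an exact linear combination of the other terms.
3. The estimated τ is therefore 0, and the ratio is exp(0) = 1.
4. The residual variance is 0, so the standard error of τ is 0 and the 90% CI is exp(0 ± t × 0), which runs from 1 to 1. A likelihood-based procedure such as PROC MIXED may instead stop on the zero variance.

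**Numerical check.** One simulated data set per true ratio, 280 patients, fitted by least squares, first with the printed covariate and then with a pre-randomization Cmin covariate. The log-scale SDs (0.6 between patients, 0.4 residual) are assumptions. They affect only the last column.

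| True ratio | Printed model: ratio (90% CI) | Pre-randomization covariate: ratio (90% CI) |
|---|---|---|
| 1.00 | 1.000000 (1.000000-1.000000) | 1.035 (0.959-1.117) |
| 0.935 | 1.000000 (1.000000-1.000000) | 0.907 (0.838-0.981) |
| 0.80 | 1.000000 (1.000000-1.000000) | 0.847 (0.778-0.923) |
| 0.70 | 1.000000 (1.000000-1.000000) | 0.718 (0.659-0.781) |
| 0.50 | 1.000000 (1.000000-1.000000) | 0.502 (0.466-0.541) |

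With the printed covariate, the residual variance was of the order of 1e-27, which is rounding error.

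**What the repaired analysis could show.** The inputs are 280 evaluable patients (SAP section 4), taken as 140 per arm. The model has five coefficients, so there are 280 − 5 = 275 degrees of freedom. Ignoring the small loss from covariate imbalance, the 90% limits are the ratio multiplied and divided by

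exp[ t(0.95, 275) × √ln(1 + CV²) × √(2/140) ].

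| Residual CV | Factor | 90% CI around a ratio of 1 |
|---|---|---|
| 38% | exp(0.0724) = 1.075 | 93.0-107.5% |
| 60% | exp(0.1094) = 1.116 | 89.6-111.6% |
| 80% | exp(0.1387) = 1.149 | 87.0-114.9% |

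The 38% is the SAP's planning value for AUC and Cmax. The documents give no CV for Cmin, so all three rows are assumptions. They show only that a correctly specified model would be informative.

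**Whether another passage supplies the right term.** Section 20.2.7 and the protocol synopsis name Week 10-12 covariates for AUC and Cmax only. Section 20.2.8 refers back to the primary analysis without naming a covariate, and section 20.2.2 defines Cmin for Weeks 26-28 only. These passages contradict the printed term and point to Cmin,10-12, but none of them states it.

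**The case against.** The best reply is that this is an evident misprint. AUC and Cmax both take Week 10-12 values, section 20.2.9 calls the model similar to the primary one, and both documents treat covariates as pre-randomization. A competent programmer would read Cmin,10-12, and a ratio of exactly 1 with no width could not pass for a real result. Cmin is secondary with no equivalence criterion, and the protocol synopsis does not ask for a log-scale Cmin analysis at all. AUC and Cmax at Weeks 10-12 have no formal definition in SAP 20.2.1 or 20.2.2 either. The full protocol body is not visible, and the sponsor procedure that section 20.1 cites for parameter calculation might cover the definition.

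Most of this stands, and it limits the importance of the point. It does not make the equation right. This is the operative specification of an analysis, and the correct term has to be inferred. The inference also leaves a choice open: section 20.1 extrapolates a missing Week 12 or Week 28 concentration without saying whether that value may count as a minimum observed concentration. The untransformed Cmin model in 20.2.8 is not degenerate, but its covariate is implied rather than stated, so it should be named at the same time.

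**Conclusion.** The concern holds. As printed, the log-scale Cmin model must return a treatment ratio of 1 with zero residual variance, or fail, for any data set. This is an algebraic identity and rests on no assumption about variability or sample size.

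The consequence is small. One sensitivity analysis of one secondary endpoint is lost. The co-primary models and their decision rule, the AUC and Cmax log-scale models, and the sample size do not depend on it. The case for correction rests on the certainty of the error and the ease of repair, not on any threat to the trial's main conclusion. That the intended term was Cmin,10-12 is an inference, though a strong one.

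**What to change.** Make three text changes, before unblinding:

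1. **SAP 20.2.9:** replace Cmin,26-28 on the right-hand side with Cmin,10-12, log-transformed like the other two PK covariates.
2. **SAP 20.2:** define Cmin,10-12 as the lowest observed adalimumab concentration in the Week 10-12 intensive sampling interval, derived by the same rules as Cmin,26-28. State for both intervals whether an extrapolated end-of-interval concentration is eligible. Note that the run-in interval has fewer samples; section 20.2.3 shows the two sets of sub-visits ("If actual PK sampling time for sub-visits 6a-c or 14a-f is missing"). Both arms share the same run-in schedule, so the sparser sampling does not favour either arm.
3. **SAP 20.2.8:** name untransformed Cmin,10-12 as the baseline covariate for the untransformed Cmin model.

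The cost is one term, one definition and one clause. No new data are needed, because section 20.1 already sets out rules "for each intensive PK intervals (Week 10-12 and Week 26-28").

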# APPENDIX 1. Programming Conventions for Outputs

# **IQVIA Output Conventions**

Outputs will be presented according to the following:

Use the following document as a guide and copy ONLY the relevant sections into this appendix. Make sure that once the customer agrees with the contents of this appendix, the templates/shells follow exactly what is written here.

Global Bios > Processes > GBIOS Processes - Implementation Guidelines and Templates > General Guidelines and Templates > Output Conventions.

